### **7.5.7. Clinical Laboratory Data**

The Lab shift from baseline table will be displayed by treatment arm at End of Induction, End of Consolidation and End of Study for each laboratory test.

Laboratory results will be graded by CTCAE (v5.0) and summary the maximum grade in each lab category.

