### 5.2 Treatment and Administration Schedule

End of Cycle = Count Recovery

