## 10. Study Parameters

- Pre-study assessments should be done  $\leq$  48 hours prior to randomization (except for bone marrow biopsy, thyroid function testing, pregnancy testing, ECG and left ventricular ejection fraction which can be done  $\leq$  2 weeks).

Procedures	Pre-screen	Screening/ Prior to Randomization	Induction*					Consolidation*			End of Treatment 	Follow- Up 
			Daily	Weekly	Day 21 from Start of Cycle 1 Induction	Prior to 2 nd Induction, if applicable	End of Induction	Prior to Each Consolidation Cycle	Weekly	End of Consolidation Cycle 1		
Written Informed Consent	X 	X										
Disease Characteristics 		X										
Medical/Surgical History		X										
Assessment of Baseline Signs & Symptoms		X										
Height		X										
Physical Exam		X	X 			X		X	X 		X	
Vital Signs (Temperature, Pulse, Blood Pressure)		X	X 			X		X			X	
Weight 		X				X		X			X	
BSA		X				X		X				
Performance Status		X		X		X		X			X	
CBC/Differential/ Platelets 		X	X 			X		X	X 		X	
Chemistry 		X		X 		X		X	X 		X	
Liver Functions 		X		X 		X		X	X 		X	
Thyroid Function Tests (T4 & TSH) 		X									X	
Serum Pregnancy Test 		X										
Left Ventricular Ejection Fraction (MUGA or ECHO) 		X				X 						

Procedures	Pre-screen	Screening/ Prior to Randomization	Induction*					Consolidation*			End of Treatment 	Follow- Up 
			Daily	Weekly	Day 21 from Start of Cycle 1 Induction	Prior to 2 nd Induction, if applicable	End of Induction	Prior to Each Consolidation Cycle	Weekly	End of Consolidation Cycle 1		
12-Lead ECG (QTcF Interval) 		X 		X 	X 	X 			X 		X 	
Local Bone Marrow Aspirate/Biopsy (Mandatory)	X 				X 		X 			X	X  Optional	X 
Research Bone Marrow Samples Submission (Mandatory) 	X 						X			X		X 
Protocol Therapy Administration 			X					X				
Concomitant Medications 		X	X 			X		X			X	
Adverse Events Assessment			X 			X		X			X 	
Survival Status												X

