\* **Scheduled Visits:** Delay due to holidays, weekends, bad weather or other unforeseen circumstances will be permitted.

\*\* If prophylactic lumbar puncture is performed, recommend scheduling so results are available prior to Day 8 or wait until Day 21 to perform.

1 Any patient undergoing bone marrow biopsy with suspicion of or known diagnosis of AML will be asked to sign a Prescreening Consent in order to obtain baseline immunophenotyping and determination/confirmation of FLT3 status and obtain research samples for the study prior to randomization. FLT3 (includes signal ratio), NPM1 and DNMT3 mutation status will be performed on all patients. These tests will be completed at Central Labs. See Section 13.1, Invivoscribe Lab Manual and PrE0905 Lab Manual for details. **FLT3 and NPM1 mutation status results must be available on all patients.** Patients must have known FLT3 mutation and will be stratified according to TKD vs. ITD FLT3 mutation. Patients with FLT3-ITD mutation will undergo further stratification with NPM1 mutation status (positive vs. negative) and signal ratio (high [ $\geq 0.5$ ] vs. low [ $<0.5$ ] of FLT3 Wild Type).

For patients who are registered with tissue submitted for the study and are FLT3 negative or other condition, no further information will be collected after baseline demographics, sample submission, sample results and final diagnosis.

2. Record date of diagnosis (date of diagnostic bone marrow biopsy), primary tumor type, histology, cytogenetics and molecular markers.

3 **Induction:** Daily if admitted to hospital, otherwise weekly until count recovery.

**Consolidation:** May be done locally after Day 8 visit per institutional guidelines.

4. Per Study Parameters and as clinically indicated.

5 CBC with differential and platelet count which includes WBC, ANC, Platelets, Hemoglobin, and Hematocrit. Additionally, required within 24 hours prior to each cycle of chemotherapy.

- 
- 6 **Induction:** Differential daily until disappearance of peripheral blasts, then twice weekly at nadir, after peripheral blasts gone and while WBC <500. If the patient is discharged prior to recovery of WBC ( $\geq 500$ ), obtain differential twice weekly until end of induction, then per institutional guidelines until consolidation starts.  
**Consolidation:** Twice weekly or per institutional guidelines.

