- 7 BUN/creatinine, uric acid, sodium, potassium, chloride, glucose, calcium, magnesium, and phosphorus. Additionally, required within 24 hours prior to each cycle of chemotherapy.
- 8 **Induction:** Twice weekly.  
**Consolidation:** Weekly or per institutional guidelines.
- 9 AST, ALT, and total bilirubin. If total bilirubin  $\geq 2$ , obtain direct bilirubin (if direct bilirubin  $\geq 2$ , refer to Section 6.1 for Dose Modifications/Interruptions). Additionally, required within 24 hours prior to each cycle of chemotherapy.
- 10 Thyroid Function test results not required for randomization.
- 11 Required for sexually active females of child-bearing potential.
- 12 LVEF must be obtained before initiating second induction cycle (if applicable) and must use same method as initial assessment.
- 13 Perform 12-lead ECG in triplicate (3 separate ECGs recorded at least 5 minutes apart) following a 10 minute resting period. Patient may not have QTcF interval >500 msec or Long QT Syndrome.  

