**ARM B**

- **Cytarabine** 3 g/m^2\* over approximately 1-3 hours every 12 hours (+/- 2 hour window) on days 1,3,5 or days 1-3 for a total of 6 doses for up to 4 cycles
- **Midostaurin** 50 mg orally BID x 14 days beginning on day 8 of each cycle (up to 4 cycles)

\* For patients age  $\geq 55$  or patients with decreased creatinine clearance recommend reducing consolidation cytarabine dose to 1.5 g/m^2.

If there is a delay in starting FLT3 inhibitors in Arm A or Arm B (due to obtaining drug, i.e. insurance, formulary, etc.), the FLT3 inhibitor will need to stop after Day 21 dose. No missed doses will be made up.

Prophylaxis with intrathecal chemotherapy is allowed prior to or during consolidation.

See Section 5 for dosing instructions and additional information for gilteritinib and midostaurin administration and Section 6 for dose delays/modifications.

**NOTE:** Patients deemed suitable by the treating investigator may proceed to allogeneic TRANSPLANT after induction or after 0-4 cycles of consolidation. Patients will go off treatment at the time of transplant or any non-protocol leukemia directed therapy after completion of the end of treatment visit.

22 Please review all concomitant medications. Section 6.2.2 for medications not permitted and Section 6.2.3 for medications to use with caution. Only record concomitant medications for SAE and/or AESI in eCRF.

23 Patients will be followed for adverse events for 30 days after their last dose of study medication. However, an adverse event occurring at any time after discontinuation of study therapy that is felt to be at least possibly related to study therapy should be recorded.

**NOTE:** Pregnancy within 180 days for WOCBP and for 120 days for a female partner of child-bearing potential after the final study drug administration will be reported and followed per Section 8.6.

- 24 Upon count recovery after last cycle of chemotherapy and completion of gilteritinib or midostaurin.

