### **6.3. Clinical Laboratory Assessments**

Clinical laboratory tests will be collected at screening, prior cycles of treatments, twice weekly during induction, weekly in consolidation, and at end of treatment.

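### The SAP's lab shift tables sit at phase ends near count recovery, so they understate nadir and resolved abnormalities; a baseline-to-worst-grade shift would correct this

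*SAP*

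**What the plan says.** SAP Section 7.5.7 has two sentences. The first sets the time points of the shift table, which is to cover every test: "The Lab shift from baseline table will be displayed by treatment arm at End of Induction, End of Consolidation and End of Study". The second adds a summary not tied to any visit: "Laboratory results will be graded by CTCAE (v5.0) and summary the maximum grade in each lab category".

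SAP Section 6.3 describes collection differently: "Clinical laboratory tests will be collected at screening, prior cycles of treatments, twice weekly during induction, weekly in consolidation, and at end of treatment". None of the three shift-table points is in that list by name.

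The protocol ties the end of a cycle to blood counts (Section 5.2): "End of Cycle = Count Recovery". It places the End of Treatment visit (Section 10, footnote 24) as follows: "Upon count recovery after last cycle of chemotherapy and completion of gilteritinib or midostaurin".

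Two general SAP rules also apply. Tables are presented by arm (Section 7.1), and safety is assessed by induction and consolidation (Section 7.5).

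**The concern.** Toxicity in each arm is a secondary objective, and the shift table is the only planned laboratory table that uses the patient's own baseline. A phase-end shift describes where patients finish, not how far they moved while on treatment. If the value used is taken once counts have recovered, cytopenia at the nadir and a transaminase rise that came and went during dosing leave no trace in it. Raised liver transaminases are a listed gilteritinib risk (protocol Section 11.1.9.3), so a transient rise is something the comparison should be able to show.

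There is also a programming problem. Without a scheduled draw, a window or a definition of End of Study, two programmers could build different tables from the same data.

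**Working it through.** No power or sample size figure bears on this point. The check compares the schedules and texts, with one subtraction.

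**Step 1. Schedule marks.** Protocol Section 10 and SAP Appendix I give the same pattern for these rows. The SAP heads its column End of Consolidation; the protocol heads it End of Consolidation Cycle 1.

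| Tests | Screening | During cycles | Before second induction and each consolidation cycle | End of Induction | End of Consolidation (Cycle 1) | End of Treatment | Follow-Up |
|---|---|---|---|---|---|---|---|
| Blood counts | yes | yes | yes | none | none | yes | none |
| Chemistry | yes | yes | yes | none | none | yes | none |
| Liver | yes | yes | yes | none | none | yes | none |
| T4/TSH | yes | none | none | none | none | yes | none |

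The two phase-end columns have no laboratory marks. Neither schedule has a column called End of Study. The only scheduled post-baseline point for T4/TSH is End of Treatment.

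**Step 2. Which draws could stand in.** There are several:
- Chemistry and liver tests are twice weekly in induction (footnote 8).
- For patients discharged before white cell recovery, footnote 6 says: "obtain differential twice weekly until end of induction, then per institutional guidelines until consolidation starts".
- Counts, chemistry and liver tests carry a pre-cycle rule (footnotes 5, 7 and 9): "Additionally, required within 24 hours prior to each cycle of chemotherapy".
- End of Treatment has all four groups.

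Nearby values therefore exist. SAP Section 7.2 covers repeats within a visit and says that missing data are not imputed. It has no rule assigning a draw to a phase end.

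**Step 3. When those draws fall.** Count recovery means ANC at least 1000/mm³ and platelets at least 100,000/mm³ (protocol Section 5.2.1; SAP Section 5.5). The FLT3 inhibitor stops after the Day 21 dose, or Day 22 if started on Day 9. The end-of-induction marrow is due by Day 60 of the last induction cycle. The longest gap is:

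- 60 − 21 = 39 days
- 60 − 22 = 38 days

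This is an upper limit, and patients who recover sooner have a shorter gap. End of Treatment is also set at count recovery, so reading End of Study as End of Treatment gives the table a scheduled draw but not an on-drug one.

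**Step 4. What each output can show.** Take three illustrative patients with the same liver test.

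| Patient | Phase-end shift | Maximum grade | Baseline to worst grade |
|---|---|---|---|
| Normal at entry, Grade 3 during dosing, normal at phase end | normal to normal | Grade 3 | normal to Grade 3 |
| Grade 3 at entry, never worse, normal at phase end | Grade 3 to normal | Grade 3 if the entry value is counted, or if still Grade 3 at a later draw | Grade 3 to worst later grade |
| Normal at entry, Grade 3 at phase end | normal to Grade 3 | Grade 3 | normal to Grade 3 |

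The phase-end shift misses the first patient's event. The maximum grade catches it but can put the second patient in the same cell. Only the last column separates them. Such entry values are possible: criterion 3.11 allows ALT or AST above 3 times ULN when secondary to leukemia, and bilirubin of 2 mg/dL or more with leukemic infiltration.

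**The case against.** The strongest reply is that the section already has its safeguard. The maximum-grade sentence uses graded results without limiting them to a visit, so it captures nadir and transient values. Read with SAP Sections 7.1 and 7.5, it would be shown by arm and by phase. Protocol Section 8.1 also records Grade 3 or higher changes from baseline as adverse events, including laboratory abnormalities, and SAP Section 7.5.6 tabulates treatment-related events by arm and phase. Table layouts are in a separate template that is not among the documents, and visit mapping may be given there.

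Much of this stands. A reader might infer from the blank columns that no laboratory data exist at these points, that all thyroid cells would be empty, or that the tables cannot show toxicity. The documents do not support those readings:
- Induction, pre-cycle and End of Treatment draws supply nearby values.
- End of Treatment can serve as the end of consolidation, or as the end of induction for a patient who leaves for transplant, and it includes T4/TSH.
- Count recovery constrains only ANC and platelets, not liver, renal or hemoglobin values.
- Not every patient has recovered. The marrow sample is taken by Day 60 regardless of counts, and CRi allows residual neutropenia or thrombocytopenia.

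The reply does not supply the missing link to baseline. The maximum-grade summary is neither tied to baseline nor stated as post-baseline. The adverse event route is narrower: recording is mainly Grade 3 or higher, SAP Section 6.1 limits laboratory events to those needing active management, and the event tables in SAP Section 7.5.6 rest on investigator attribution in an open-label trial.

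**Conclusion.** The concern holds as a minor point. The baseline-referenced shift tables are set at two phase ends with no scheduled laboratory draw and at a third point that is not a visit. The nearest draws fall at or near recovery, at the end of induction up to 38 or 39 days after the last scheduled FLT3 inhibitor dose. The tables will understate nadir and resolved on-drug abnormalities. The maximum-grade summary reduces the loss but cannot tell entry abnormality from worsening on study.

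The documents give no figure for how many abnormalities arise and resolve between dosing and phase end, so the size of the understatement is unknown. It would also be wrong to conclude that an arm difference in toxicity would go unseen, because the maximum-grade and adverse event summaries remain. The primary endpoint and the stopping rules do not depend on this table. The conclusion assumes that the unseen table template does not already specify a worst-grade shift.

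**What to change.** In SAP Section 7.5.7:

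1. Make the shift table baseline CTCAE grade against worst post-baseline grade, by arm, within induction and, among patients who received consolidation, within consolidation. Use all results on the laboratory eCRF.
2. Divide the phases as SAP Section 7.5.6 already does for adverse events, at the first dose of consolidation treatment, and name the draw that counts as baseline.
3. Keep one shift from baseline to the End of Treatment visit, which is needed for T4/TSH, and replace End of Study with End of Treatment.

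The cost is SAP wording, revised table shells and a small amount of extra programming. No new assessments are needed, because protocol Section 8.1 already sends all protocol-required laboratory results to the eCRF.

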### **7.5.8. Physical Exam Data**

All abnormal findings from physical exam are recorded in medical history, adverse event or other appropriated CRF pages. There are no data display for physical exam data.

### **7.5.9. ECG Data**

ECG data collected value and change from baseline will be summarized by treatment cycle and displayed by treatment arm and overall treatment group. For the triplicate measurements in a timepoint, the average of the 3 records will be represented for that timepoint value in analysis.

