### 1.3.2 Clinical Experience

As of the data cutoff date of 06 Jun 2018, 1 study in AML patients, 3 studies in healthy subjects, 1 study in healthy subjects and hepatic impairment subjects and 1 study in patients with solid tumors were complete. A phase 1b/2 study in combination with erlotinib in NSCLC patients was terminated. Ongoing studies include, 8 studies in AML patients, a phase 1/2 rollover study, a taste profile study in healthy subjects and 2 expanded access studies. Overall, 170 healthy subjects, 16 subjects with hepatic impairment and 931 patients have received at least 1 dose of gilteritinib.

In Study 2215-CL-0101, a Phase 1/2 study in patients with relapsed and refractory AML, gilteritinib generally exhibited linear, approximately dose-proportional pharmacokinetics after once daily administration over the dose range evaluated (20 to 450 mg). Median  $t_{max}$  was observed between 2 and 6 hours following single and repeat dosing of gilteritinib. At a dose of 120 mg once daily, the median  $C_{max}$  at day 15 was approximately 282 ng/mL (n=3) and the median  $AUC_{24}$  at day 15 was approximately 6180 ng·h/mL (n=3). After multiple dose administration, gilteritinib exhibited a long half-life, ranging from 45 to 159 hours and up to 10-fold accumulation based on the accumulation index,  $R_{ac}$ .

Results from Study 2215-CL-0101 indicate that of the 252 patients who received at least 1 dose of gilteritinib, the majority of composite complete remission (CRc) and partial remission (PR) events were observed in FLT3 mutation-positive AML patients in dose groups of 80 mg and greater. The derived response rate (CRc + PR) at the end of treatment in the 191 FLT3 mutation-positive patients was 48.7% overall and 66.7%, 53.6%, 48.3%, 60.0% and 50.0% in the 80 mg, 120 mg, 200 mg, 300 mg and 450 mg dose groups, respectively.

Refer to the Gilteritinib IB for more details.

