**Calculation of QTc interval using the Fridericia formula:**  
[https://qxmd.com/calculate/calculator\\_48/ecg-corrected-qt](https://qxmd.com/calculate/calculator_48/ecg-corrected-qt)
- 14 Perform 12-lead ECG in triplicate (3 separate ECGs recorded at least 5 minutes apart) following a 10 minute resting period prior to gilteritinib or midostaurin administration (ECG within 1 hour of dosing preferred). The mean QTcF of the triplicate ECG tracings will be used for final treatment decisions and AE reporting. If the mean of the triplicate QTcF is >500 msec, then triplicate ECGs will be repeated (within 2 hours). If the repeat ECGs confirm a mean QTcF >500 msec, refer to Section 6.1.2 and Section 6.1.3 for further guidance on treatment decision. In addition, on Cycle 1, Day 15 if QTcF is increased >30 msec over screening, repeat ECG on Day 16 and refer to Section 6.1.2 for further guidance on treatment decision.
- Induction (First Induction)**  
Day 8, Day 15 and Day 21
- Second Induction and Consolidation**  
Day 8 of each cycle
- See footnote 13 for Calculation of QTc interval using the Fridericia formula.**
- 15 Perform 12-lead ECG in triplicate (3 separate ECGs recorded at least 5 minutes apart) following a 10 minute resting period.  

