### **7.1. Methodology**

In general, listings will be presented by patient. Tables will be summarized and presented by treatment arm in specific analysis populations.

The results of this study will be reported using summary tables, figures, and data listings. Continuous variables will be summarized using mean, SD, median, minimum, and maximum. Categorical variables will be summarized by presenting the number (frequency) and percentage in each treatment arm.

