### Second Induction and Consolidation

Day 1 of each cycle

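### The ECG section of the SAP commits to by-cycle summaries only, with no count of patients above a QTcF level and no display by day within first induction

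*SAP*

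**What the plan says.** SAP 7.5.9 has two sentences. The first reads "ECG data collected value and change from baseline will be summarized by treatment cycle and displayed by treatment arm and overall treatment group". The second says that triplicate tracings are averaged to give the value for a timepoint. SAP 7.1 supplies the statistics: "Continuous variables will be summarized using mean, SD, median, minimum, and maximum". Neither section names a QTcF level, a category of change, a per-patient maximum or a day within a cycle.

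The ECG schedule is in footnote 14 to the study parameters (protocol Section 10). Triplicates are recorded "following a 10 minute resting period prior to gilteritinib or midostaurin administration (ECG within 1 hour of dosing preferred"). In first induction they fall on "Day 8, Day 15 and Day 21". In second induction and consolidation the protocol says "Day 8 of each cycle", whereas SAP Appendix I says "Day 1 of each cycle". There is also an ECG at end of treatment, which footnote 24 times as "Upon count recovery after last cycle of chemotherapy and completion of gilteritinib or midostaurin".

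Protocol 11.1.9.2 describes the QT risk by patient: in earlier relapsed/refractory experience, 4.4% had a maximum post-baseline QTcF above 500 ms and about 8.8% had a change above 60 ms. Protocol 1.3.1 gives these rates alongside a predicted mean change below 10 ms at the 120 mg dose. Dose rules apply above 500 ms in both arms (6.1.2, 6.1.3). Table 6-3 for gilteritinib adds a rule for a rise above 30 ms on Day 15.

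**The concern.** QT prolongation is a risk the protocol names for gilteritinib, and ECG monitoring was put in place because of it. The protocol measures that risk by how many patients reach a threshold. A mean and SD by cycle do not answer that, and a maximum shows that at least one patient crossed a level, not how many did.

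The choice of cycle as the reporting unit also matters, because the first-induction ECGs differ in kind. One is taken before any FLT3 inhibitor and two are taken during dosing. If the days are not shown separately, the reader cannot see the change on drug.

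The SAP text does plan patient-level QT information in the adverse event tables of 7.5.6. Those tables are restricted to events the investigator judged related, in a trial where the investigator knows the arm. At stake is how clearly the report shows QT outliers by arm.

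**Working it through.** The plan states no figure to reproduce here, so the check sets the schedule against the dosing calendar and then gives a sense of scale.

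**Step 1: which scheduled ECGs are on drug.** Both inhibitors run for 14 days from Day 8 (protocol 5.2.1), that is, Days 8 to 21, and each ECG precedes that day's dose.
- First-induction Day 8: before the first dose, so no study inhibitor on board.
- First-induction Days 15 and 21: during the dosing course.
- Second induction and consolidation: Day 8 by the protocol, before that cycle's first dose. Day 1, as in the SAP appendix, would also precede it. These ECGs are pre-dose for their cycle but not necessarily drug-free, since "gilteritinib exhibited a long half-life, ranging from 45 to 159 hours" (protocol 1.3.2).
- End of treatment: after the inhibitor is completed.

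This is the planned calendar. Protocol 5.2.1 allows a delayed inhibitor start when drug access is slow, so a given patient's Day 15 ECG could still be pre-drug.

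**Step 2: the on-drug share.** Scheduled post-screening ECGs per patient = 3 (first induction) + s (0 or 1 second induction) + c (0 to 4 consolidation cycles) + 1 (end of treatment).
- Minimum: 3 + 0 + 0 + 1 = 4, so 2/4 = 50% on drug.
- Maximum: 3 + 1 + 4 + 1 = 9, so 2/9 = 22% on drug.

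**Step 3: how many patients a count might show.** Take 170/2 = 85 eligible patients in the gilteritinib arm. Assume that the earlier rates carry over; they come from a different population.
- Above 500 ms: 85 × 0.044 = 3.7 patients. Chance of at least one: 1 − 0.956^85 = 97.8%.
- Change above 60 ms: 85 × 0.088 = 7.5 patients. Chance of at least one: 1 − 0.912^85 = over 99.9%.
- At half those rates: 85 × 0.022 = 1.9 and 85 × 0.044 = 3.7 patients.

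These are small numbers that a table of patients shows directly and a cycle mean does not.

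**Step 4: what else in the SAP could supply the count.**
- SAP 7.5.6 tabulates related events by preferred term and each patient's worst grade of related non-hematological event. A crossing judged unrelated is absent.
- SAP 7.5.7 summarizes maximum CTCAE grade, but for laboratory results only.
- SAP 7.1 plans listings by patient, from which a reader could count by hand.
- The document history records that ECG analysis was split into induction and consolidation. That does not separate Day 8 from Days 15 and 21.

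**The case against.** The strongest reply is that the table shells are a separate document. SAP 2.1 places the detailed description of displays there, and threshold categories and visit rows are the kind of detail shells hold. The document history shows the shells being revised together with the ECG analysis. This stands: the table may already exist, and the point is then only that 7.5.9 should say so.

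A reader might infer that Days 8, 15 and 21 will be averaged into one cycle value, diluting the drug effect. The documents do not support that. SAP 7.5.9 refers to a value for each timepoint, and SAP 7.2 keeps the first measurement at a visit when safety data are repeated. Visit-level values arranged by cycle are at least as natural a reading. What can be said is that display by day is not stated.

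A reader might also infer that QT outliers would be hidden. That goes too far. The planned maximum would reveal an extreme value, and the listings show individual patients. Protocol 8.1 requires QTc events that meet dose-action criteria to be recorded even below Grade 3, and SAP 7.2 counts an event with missing relationship as related. The limitation left is that the planned tables depend on attribution and the listings give no count by arm.

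Finally, because the 30 ms rule is only in the gilteritinib table, a reader might suspect that QTc events are recorded differently by arm. This is not established: the Day 15 and 16 repeat-ECG instruction in footnote 14 is not restricted to one arm.

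**Conclusion.** The point holds as a gap in what the SAP text commits to: no count of patients above a QTcF level, no display by day in first induction, and patient-level QT tables limited to events attributed by open-label investigators. The protocol's own threshold language makes a count the natural summary, and the data are already collected.

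It is an optional improvement in reporting. It should not be read as a failure to meet the toxicity objective, because protocol 12.2.2 defines toxicity as related adverse events and SAP 7.5.6 tabulates those. Efficacy, dosing and safety monitoring are unaffected. The difference between Day 1 and Day 8 in the SAP appendix is real but clerical.

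The on-drug share of 2 of 4 to 2 of 9 rests on the scheduled days and an on-time inhibitor start. The expected 3.7 and 7.5 patients rest on earlier rates carrying over and are for scale only. Confidence is medium, because the shells are not available.

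**What to change.** Add one descriptive table to SAP 7.5.9, by arm in the safety population and regardless of attribution. Give n (%) of patients with triplicate-mean QTcF above 500 ms, and with an increase from screening above 30 ms and above 60 ms:
- at scheduled first-induction Days 15 and 21, as the leading display;
- as the maximum over ECGs taken after the patient's actual first inhibitor dose, with the number who have no such ECG.

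State these rules with it:
- Classify an ECG as on drug by actual dosing dates, since delayed starts are allowed.
- Use the first triplicate mean at each visit, in line with SAP 7.2, or state an exception for the maximum.
- Show first-induction change by day (8, 15, 21).
- Change the later-cycle ECG day in SAP Appendix I from Day 1 to Day 8.

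If the shells already contain this table, a sentence in 7.5.9 saying so is enough, alongside the appendix correction.

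The cost is some SAP wording and one extra table from triplicates already collected. The one analytic drawback is that maxima including unscheduled or confirmatory ECGs may be unbalanced between open-label arms, which is why the scheduled-day counts should lead.
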